#### **3.6.5 Sensitivity Analyses**

The following sensitivity analyses will be performed on the primary endpoint.

- The difference between treatment groups with regards to time till death using all available information including follow-up will be assessed using a log rank test stratified by pooled site ([Peduzzi, Henderson, Hartigan, and Lavori \(2002\)](#)).

- The analysis specified for the primary endpoint will be done with no imputation for missing data.
- The analysis specified for the primary endpoint will be done assuming all subjects with unknown mortality status at day 28 are alive.

Additional sensitivity analyses which will be performed only for the interim analyses are detailed in [section 3.8](#).

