### **2.2 Decision Guidelines**

The primary analysis of this Phase 3 trial is formally based on a two-category decision guideline. Specifically, the decision guideline for this trial is based on whether the observed two-sided p-value associated with comparison of the 28-day survival for the ART-123 arm vs. the placebo arm is, between 0.05 and 0.001 or less than 0.001.

1. If the two-sided p-value is between 5% and 0.1% then the ART-123-based regimen will have met the generally accepted level of evidence (false positive error rate) required to demonstrate efficacy.
2. If the two-sided p-value is less than 0.1% and supporting analyses corroborate this finding, the ART-123-based regimen will have provided highly reliable and statistically strong mortality results in a disease with limited treatment options. A second confirmatory study would then not be required.

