### **2.3 Sample Size**

The primary analysis for this study will be based on a stratified Cochran-Mantel-Haenszel test. For sample size and power calculations a Chi-squared test has been used. A sample size of 800 subjects provides approximately 80% power if the following assumptions are made:

1. 5% two-sided alpha level
2. 8% treatment effect (24% placebo mortality rate vs. 16% ART-123 mortality rate).
3. 1 to 1 randomization

The assumed treatment effect and mortality rates are based upon post-hoc results from study 2-001 and assume the day 28 mortality status will be known for all subjects.

A sample size of 800 subjects and these assumptions also provides 32% power for a 0.1% two-sided  $\alpha$  level. If the true treatment effect is 12% (24% vs. 12%), a sample size of 800 provides greater than 80% power when a 0.1% alpha level is used.

In this 800 subject study, an observed treatment benefit of approximately 6% is expected to result in a p-value less than 5% and a difference of approximately 9% is expected to result in a p-value less than 0.1%.

The sample size and power calculations were performed with Pass 2007.

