### **3.6.2 Long Term Mortality Status**

Long term mortality status will be determined at 3, 6 and 12 months after start of treatment. This information will not be available for all subjects at the time of primary database lock. The analysis of long term mortality status will include Kaplan Meier based summarization of mortality rates at 3, 6 and 12 months as well as Kaplan Meier plots of time until death. Differences between treatment arms will be tested with a log rank test stratified by pooled site.

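### The only time-to-event sensitivity analysis of 28-day mortality runs on all follow-up, and no log-rank test censored at Day 28 is planned

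*SAP*

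**What the plan says.** SAP 3.6.5 names three sensitivity analyses of the primary endpoint, which is all-cause mortality at 28 days. In the first, "time till death using all available information including follow-up will be assessed using a log rank test stratified by pooled site". The other two repeat the binary Day 28 analysis and change only how unknown status is handled: one imputes nothing, the other counts every unknown as alive.

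SAP 4.3.1, in the text that follows the subgroup list in 4.3.1.1, makes the horizon explicit. The log-rank test takes in all mortality data available at the cut and does not stop at Mortality Day 28. Subjects without a death record are censored when last known alive. That paragraph also describes the test as stratified by treatment.

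SAP 3.6.2 covers mortality at 3, 6 and 12 months and says: "Differences between treatment arms will be tested with a log rank test stratified by pooled site".

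The remaining time-to-event material does not fill the gap. The Kaplan-Meier estimate at Mortality Day 28 (SAP 3.6.1) is descriptive, and the stratified log-rank test in Protocol 10.5.2 has no stated horizon.

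SAP 2.2 gives the supporting analyses a role in the stronger of its two decision categories, which opens: "If the two-sided p-value is less than 0.1% and supporting analyses corroborate this finding". In that category a second confirmatory study would not be required.

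**The concern.** A sensitivity analysis should put the primary question again under different assumptions. This one puts another question, survival over up to 12 months, and it coincides in test and strata with the long-term analysis. If it disagrees with the primary result, the reader cannot tell whether the 28-day finding is fragile or whether later deaths have diluted or eroded it.

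What is missing is a test that keeps the 28-day horizon, uses the death times, and treats unknown status by censoring instead of by imputing or leaving the subject out. At stake is the reading of the supporting evidence when the primary p-value falls below 0.001, because SAP 2.2 then asks for corroboration without saying which analyses count or at what level.

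**Working it through.** **Inputs from SAP 2.3.** "5% two-sided alpha level"; "8% treatment effect (24% placebo mortality rate vs. 16% ART-123 mortality rate"; "1 to 1 randomization", so 400 per arm.

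**The plan's own figures.** The SAP states "A sample size of 800 subjects provides approximately 80% power" and "A sample size of 800 subjects and these assumptions also provides 32% power for a 0.1% two-sided" alpha level. Pooled rate = 0.20.

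- SE under the null = √(0.20 × 0.80 × 2/400) = 0.02828.
- SE under the alternative = √(0.24 × 0.76/400 + 0.16 × 0.84/400) = 0.02814.
- Power at 0.05 = Φ((0.08 − 1.960 × 0.02828)/0.02814) = Φ(0.873) = 0.809.
- Power at 0.001 = Φ((0.08 − 3.2905 × 0.02828)/0.02814) = Φ(−0.464) = 0.321.

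Both agree with the SAP.

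**Log-rank test censored at Day 28.** With constant hazards to Day 28, HR = ln(0.84)/ln(0.76) = 0.635. Expected deaths = 96 + 64 = 160. By the Schoenfeld formula, z = |ln 0.635| × √160/2 = 2.869. Power is Φ(2.869 − 1.960) = 0.818 at 0.05 and Φ(2.869 − 3.2905) = 0.337 at 0.001, close to the primary test.

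**The planned test, by approximation.** The documents give no mortality rate after Day 28, so a range is assumed. Expected Day 28 survivors are 304 on placebo and 336 on ART-123, 640 in all. If a fraction q of them die by Day 360 at the same rate in both arms, these 640q deaths add variance but no signal. The expected z therefore shrinks to about 2.869 × √(160/(160 + 640q)). At q = 10% this is 2.869 × √(160/224) = 2.425, and power is Φ(0.465) = 0.679.

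**The planned test, by simulation.** There were 3,000 trials per scenario, 400 per arm, with hazards constant before and after Day 28 and an unstratified log-rank test at two-sided 0.05. Simulation error on a power of 0.6 is √(0.6 × 0.4/3000), about 0.9 points. Data cut at lock means uniform entry over six years (Protocol synopsis: 3Q 2012 to 3Q 2018), with the cut at the primary database lock.

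| Late mortality, both arms | Approximation | Full 12 months | Data cut at lock | Non-significant given primary p<0.05 (cut at lock) |
|---|---|---|---|---|
| 5% | 0.745 | 74% | 73% | 12% |
| 10% | 0.679 | 68% | 68% | 18% |
| 15% | 0.621 | 60% | 63% | 25% |
| 20% | 0.571 | 55% | 57% | 33% |

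The Day 28-censored log-rank had about 81% power throughout and was non-significant in about 1% of trials with a significant primary test. A repeat of the data-cut runs gave 74, 67, 62 and 59% for the planned test.

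**Given primary p<0.001.** With equal late mortality, the planned test misses 0.05 in about 0 to 8% of trials when data are cut at lock, and in 0.2, 1.7, 5.7 and 10.1% with full 12-month data.

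**Unequal late mortality (also assumed).**

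- Partial catch-up, 10% placebo vs 15% ART-123: power about 23 to 25%. Given primary p<0.001, about 39% miss 0.05 with the cut at lock, and 42% with full data.
- Full catch-up, 10% vs 18.6%: 12-month mortality is equal, since 0.24 + 0.76 × 0.10 = 0.316 and 0.16 + 0.84 × 0.186 = 0.316. Power is about 6 to 7%, and the statistic favours placebo in about a third of trials.
- Benefit continuing, 10% vs 8%: power about 82%, no loss.

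With equal late mortality the statistic favours placebo in about 0.5 to 2% of all trials.

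**The case against.** The horizon is a deliberate choice, since SAP 4.3.1 spells it out. The primary objective speaks of reducing mortality in general, and 3-month mortality is a secondary endpoint. If late deaths are higher on ART-123, a weak all-follow-up test shows that the benefit is eroding, which is relevant to waiving a second study. The 3.6.2 results are incomplete at primary lock, so deleting the test from 3.6.5 would remove the durability check when the decision is taken. All of this stands, and it argues for adding a Day 28 test instead of replacing the planned one.

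It can also be said that the added test would nearly always agree with the primary test, and that 3.6.5 already varies the imputation. The first part is correct and limits the gain. The second is only partly an answer: neither binary variant censors a subject at last contact, and the Day 28 Kaplan-Meier estimate carries no test.

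A reader might infer that the planned test would often contradict a true 28-day effect, or often block the stronger decision category. The figures do not support this. With equal late mortality the usual effect is lost significance, and a reversed direction is rare. Once the primary p-value is below 0.001, failure at 0.05 is uncommon unless late deaths are in excess on ART-123. Failure would be frequent (32 to 66% with equal late mortality) only if corroboration meant p<0.001 on this test as well, and SAP 2.2 sets no such threshold and refers to supporting analyses in the plural. A reader might also suspect that the date of the data cut drives the result. With about six years of entry it matters little, as the two simulated columns show.

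**Conclusion.** The point holds as a modest one. The test in SAP 3.6.5 is a long-term survival analysis listed as a sensitivity analysis of the 28-day endpoint, and no Day 28-censored log-rank test is planned. With true rates of 24% and 16% and equal late mortality of 5 to 20%, its power is about 73% falling to 57% against about 81%, and it leaves about 12 to 33% of significant primary results without nominal support. In the category where SAP 2.2 asks for corroboration, the shortfall is about 0 to 8%, or about 39% with 10% vs 15% late deaths. It vanishes if the benefit continues.

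All these figures rest on assumed late mortality, constant hazards within each period and an unstratified test. The primary test, its alpha and its estimate are not affected. The change is worth making because it is cheap and supplies a supporting test of the right question.

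**What to change.** - **SAP 3.6.5:** add a log-rank test of time from first dose to death, stratified by pooled site. Censor survivors at Mortality Day 28 and subjects with unknown status at last contact, without imputation. Count deaths by the same 28-day rule as in SAP 3.6.1.
- **All-follow-up test:** keep it, but label it as evidence on long-term survival or durability, not as a sensitivity analysis of the 28-day endpoint.
- **SAP 4.3.1:** align the log-rank paragraph with both tests. Correct its stratification factor, which is given as treatment and conflicts with pooled site in 3.6.2 and 3.6.5.

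The change should be made before unblinding, so that the supporting test is not chosen with results in hand. The cost is a few lines of SAP text and one program call. The downside is one more analysis, which will usually agree closely with the primary test.

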### 3.7 Safety Analyses

Safety endpoints will be summarized as outlined in [Section 4.4](#). Testing will not be utilized. Confidence intervals will be produced for major bleeding events as discussed in [section 4.4.6](#).

### 3.8 Interim Analysis

This study will include un-blinded interim analysis (IA) performed by a Data Monitoring Committee. There will be 4 IAs planned to occur when 150, 300, 450 and 600 subjects are evaluable for the 28 day all-cause mortality endpoint.

The DMC may recommend termination or modification of the study based upon a review of the totality of the data. Early termination of the study for efficacy will not be actively pursued however guidelines regarding this are provided in [Section 5](#).

Analyses to rule out clinically meaningful benefit will also be performed. The goal of these analyses is to stop the study if sufficient evidence exists that there is not a clinically meaningful treatment benefit. The futility analyses will be conducted with the use of a lower O'Brien-Fleming-type boundary. This boundary will be constructed using a one-sided alpha level of 0.20 and will test the hypothesis given below:

$$H_o : M_{ART} < M_{plb} - 6\%$$
$$H_a : M_{ART} \geq M_{plb} - 6\%$$

Confidence intervals will be used to evaluate these hypotheses as outlined in [Section 5](#).

Termination or modification of the study due to safety concerns will not be limited to a fixed set of analyses.

## **4 STATISTICAL SUMMARIES**

### **4.1 General Conventions**

Summary statistics will be presented by treatment group and overall.

Categorical data will be summarized and presented using counts and percentages for each treatment group. For categorical data, the percentage will be suppressed when the count is zero to highlight the non-zero results. The denominator for all percentages, unless otherwise specified, will be the number of subjects in each treatment group or overall within the analysis population.

For continuous variables, summary statistics will consist of the number of observations, mean, median, standard deviation, minimum, and maximum. All minimum and maximum values will be displayed with the same number of decimal places relative to the raw data, the mean and median will each have one additional decimal place, and the standard deviation will be displayed with two additional decimal places.

The trial period is divided into an active treatment period, defined as the dosing period followed by post-dose follow up, and a subsequent long-term follow up period see [Section 5.2.1](#) of the Protocol, Table 1: Visit Schedule and Assessments.

All visits including unscheduled visits through 28 days will be re-mapped or derived according to the windowing algorithm in [Table 1](#) and subject to rules laid out in [Section 2.3](#). Presentation of summary measures will be by nominal time points corresponding to the remapped visits as seen in [Table 1](#).

Any deviations from the originally planned analysis as specified in the Protocol will be detailed in the final clinical study report with an explanation of the alternative methods employed.

### **4.2 Study Population Summary**

A table summarizing the number and percent of subjects by study population, Consented, Randomized, Safety, and Full Analysis Set will be provided by treatment group for all subjects screened. This summary will be broken down by treatment group for all subjects.

#### **4.2.1 Subject Disposition**

Subject disposition for FAS will be summarized through day 28 by randomized treatment group and overall. Two summary tables will be presented; one for study disposition and one for treatment disposition. The count and percent of subjects who completed the study through day 28 will be presented along with the reason for study discontinuation by treatment group and overall. Similarly, the treatment disposition table will include the count and percent of subjects which completed all six (6) study treatments and the reason for treatment discontinuation

A listing will present data concerning subject disposition on the FAS.

## **4.2.2 Protocol Deviations**

### **4.2.2.1 Major Protocol Deviations**

Major protocol deviations will be summarized. Major protocol deviations are

- Violations of an entry criteria.
- Incorrect treatment received.
- On treatment prohibited medication use as identified by a blinded sponsor review of medications
- Substantial overdose of study medication.

### **4.2.2.2 Violations of Inclusion/Exclusion Criteria**

Two (2) summary tables will be presented. One will display the count and percent of subjects who met each inclusion criterion and the other will similarly display a summary for subjects which did not meet each exclusion criterion. On each of the respective tables a count and percent of subjects meeting all inclusion criteria (or did not meet any exclusion criteria) by treatment group and overall for each of the protocol versions.

Subjects violating any Inclusion and Exclusion Criteria, along with the actual violated criteria, will also be presented in a by subject listing for all consented subjects.

## **4.2.3 Demographics and Baseline Characteristics**

Demographic data include age, age group (<65, ≥65), sex (Male, Female), race (American Indian / Alaska Native, Black / African American, Asian, Native Hawaiian / Other Pacific Islander, White, Mixed Race, Other), and ethnicity (Hispanic or Latino, Not Hispanic or Latino). Baseline characteristics include height, weight, baseline diabetes, baseline renal function (creatinine; <2 mg/dL, ≥2 mg/dL), baseline heparin use (any baseline medication with ATC of B01AB), arterial lactate (≤20 mg/dL, >20 mg/dL, and ≤55 mg/dL, >55 mg/dL), baseline renal replacement therapy (RRT), and APACHE II (Acute Physiology and Chronic Health Evaluation II) total score and the number and percentage of subjects with APACHE II total score < 25 and ≥25.

A blinded clinical review of medical history will be performed to identify subjects which are diabetic and this summary will be presented on the baseline characteristics table.

Demographics and baseline characteristics will be summarized for the FAS by treatment group and overall. All collected demographic and baseline characteristic data will also be presented on a by subject listing.

### **4.2.4 Summary of Septic Episode and Site of Infection**

The number and percent of subjects will be summarized by treatment group and overall, in the FAS population, for the primary site of infection which includes heart, intra-abdominal, lung, and urinary tract. Primary sites of infection with fewer than 30 subjects will be pooled into an

“other” category and also summarized on this table. The number and percent of subjects with a culture sample taken, the result of those taken being either positive or negative, and the method will also be summarized on this table. The number and percent of subjects, on a separate table, with a culture taken will be summarized for the status of sensitivity to tested antibiotics.

Additionally, a summary table of baseline antibiotic use will also be presented.

These data will also be presented in a by subject listing.

#### **4.2.5 Medical History**

A summary for medical history will be presented including the count and percent of subjects with a medical history record and also by body system and coded term. Furthermore, all data will be presented in a listing on the FAS.

#### **4.2.6 Prohibited Concomitant Medications**

A list of the prohibited concomitant medications for this study is found in [Appendix G](#) of the protocol. A summary table of prohibited concomitant medications will be presented for each treatment group and overall for using the FAS population. This table will include the count and percent of unique subjects having taken a prohibited medication while on study and also by drug class and preferred term. A by subject listing will also be presented.

#### **4.2.7 Prior and Concomitant Treatments**

##### **4.2.7.1 Prior and Concomitant Medications**

Prior and concomitant medications include the regular prior and concomitant medications and vasopressors. Prior and concomitant medications will be coded using the World Health Organization (WHO) drug dictionary version WHODRUG enhanced version March 2014.

Prior and concomitant medications will be summarized separately and presented by drug class and preferred term at each treatment group and overall for the safety population. The count and percent of subjects with at least one of the respective medications (prior or concomitant) and also by drug class and preferred term will be presented as the summary. Subjects will be counted only once for each drug class and preferred term if they reported more than one medication within a given preferred term.

Concomitant medications will be any medication which was administered to the subject after first dose. Prior medications are those which are known to have ended prior to first dose.

Medications that began prior to first dose and ended after first dose will be classified as both prior and concomitant medications.

Prior and concomitant medications will also be presented in listings by subjects in the safety population.

The imputation algorithm for partial and missing concomitant medication dates is provided in [Appendix A](#).

#### **4.2.7.2 Prior and Concomitant Surgeries and Interventions**

Prior surgeries and interventions will be summarized by body system and coded term and will be also presented in a listing for the FAS. The count and percent of unique subjects will be presented by treatment group and overall for the FAS population.

Concomitant surgeries and interventions include ventilation, dialysis, and blood products. These will be summarized similarly as prior surgeries and interventions on a separate table in addition to all data collected, in the coded format, on the associated CRF page and also provided in their respective by subject data listings.

#### **4.2.7.3 Vasopressor Use**

A summary table displaying the number and percentage of subjects who received each type of vasopressor concomitant medication at baseline, Study Day 1, Day 7, Day 14 and Day 28, where the analysis time-points can be found in the visit window structure presented in [Table 1](#) in this SAP, will be presented on the FAS population.

Vasopressor use will also be presented in a by subject listing.

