### 3 STATISTICAL METHODS

#### 3.1 Populations Analyzed

- Consented Population – All subjects who sign any informed consent. Subjects in the consented population will be analyzed based on the treatment group to which they were randomly assigned.
- Randomization Population – All subjects randomly assigned into a treatment arm.
- Full Analysis Set – The subset of the consented population who were randomly assigned to treatment and received at least one dose of study treatment. In this population subjects will be analyzed based upon the treatment group they were randomized to regardless of the study drug received.
- Safety Population – All subjects who received at least one dose of study treatment. In this population subjects will be analyzed based upon the study drug received. If subjects receive both ART-123 and placebo they will be included in the ART-123 group.

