#### **4.3.3.2 Organ Dysfunction**

The organ dysfunctions of interest are hepatic, renal, respiratory, and shock dysfunction.

A summary table, using the FAS population, will be presented which will include the analysis time points, baseline, Study Day 3, Study Day 7, 24 hours post last dose, Study Day 14, and Day 28 as described in the analysis visit window structure in [Section 3.3](#) of this SAP and the general definition for baseline. At each indicated time point, the number of subjects having survived to the nominal time point of the analysis visit will be presented. The denominator at each time point will be the number of subjects surviving to that particular time-point within each treatment arm or overall. The numerator will be the number of subjects with a particular organ dysfunction of interest at the time-point.

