#### **4.4.6 Bleeding Events**

A summary table for the number and percent of unique subjects with at least one major bleeding event during the 28 day study period, along with 95% exact confidence interval of the bleeding rate for each treatment and the exact risk difference between two treatment groups in bleeding rates, will be presented using the safety population. The count and percent of unique subjects experiencing at least one bleeding event by Study Days 3, 7, and 14 will be presented in the same table, but confidence intervals and risk difference will not be provided. Subjects will be counted as having experienced a major bleeding event from the earliest recorded event through all subsequent time points.

A bleeding event is considered on-treatment provided it occurs within five days past last dose. An after-treatment event is any event with an onset date of six or more days past last dose date. A summary of on-treatment and after-treatment major bleeding events will be presented by treatment arm and overall. If a subject experiences both an on-treatment and after-treatment event the subject will be counted in both summaries; that is, on-treatment and after-treatment event summaries may not be disjointed.

A similar summary will be presented for serious major bleeding events as well.

Additionally, the differences in major bleeding event rates will be presented by country, new infections, concomitant heparin use through day 7, renal function through day 7, baseline RRT, and on treatment RRT

Adverse events and serious adverse events identified as bleeding events will be summarized by primary system organ class (SOC) and preferred term (PT) for on treatment and off treatment separately.

All bleeding event data will be presented in a data listing.

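### By-visit vasopressor percentages default to the whole Full Analysis Set, so deaths before a visit window pull them down, whereas the related shock summary uses subjects alive at the time point

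*SAP*

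**What the plan says.** SAP 4.2.7.3 plans a table of the "number and percentage of subjects who received each type of vasopressor concomitant medication at baseline, Study Day 1, Day 7" and again at Days 14 and 28, using the Table 1 visit windows, and says that it "will be presented on the FAS population". It names no denominator.

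SAP 4.1 supplies one by default: "The denominator for all percentages, unless otherwise specified, will be the number of subjects in each treatment group or overall within the analysis population".

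SAP 3.1 defines the FAS as "The subset of the consented population who were randomly assigned to treatment and received at least one dose of study treatment". Being alive at a later visit is not a condition.

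For organ dysfunction by visit, which includes shock, the SAP departs from its default. Section 4.3.3.2 says: "The denominator at each time point will be the number of subjects surviving to that particular time-point". Section 3.6.4 likewise takes subjects alive on the given day and limits the numerator to them. The same section defines shock dysfunction as vasopressor use recorded on the vasopressor CRF page.

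**The concern.** Vasopressor use can be recorded only while a subject is alive. With the whole FAS as denominator, a subject who died before the window opened stays in the denominator and cannot enter the numerator, so the table treats that subject as a non-user.

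Mortality is the primary endpoint and is planned to differ between arms. The distortion would then differ between arms too, and against the arm with fewer deaths. If ART-123 lowers mortality as planned, a table with identical use among survivors would show more vasopressor use on ART-123. A reader could take that for a haemodynamic disadvantage, although it comes only from the denominator. The SAP's authors used a survivor denominator for shock, so its absence here looks like an omission.

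**Working it through.** **Inputs.**
- 28-day mortality: 24% placebo, 16% ART-123 (SAP 2.3, planning assumptions).
- 800 subjects randomized 1:1 (SAP 2.3), so 400 per arm.
- Visit windows: Day 14 from Study Day 10, Day 28 from Study Day 24 (SAP Table 1).
- Use among survivors, *u*: not in the documents. Assumed equal in both arms and ranged from 5% to 30%.

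**Step 1. Check the planning inputs.** The plan states no figure for the vasopressor table, so only the mortality assumptions can be checked against a stated result. For a chi-squared test with pooled variance and no continuity correction, power = Φ[(0.08·√400 − z·√(2·0.20·0.80)) / √(0.24·0.76 + 0.16·0.84)].
- Two-sided 5%: (1.600 − 1.960·0.5657)/0.5629 = 0.873, power 80.9% (plan: about 80%).
- Two-sided 0.1%: (1.600 − 3.291·0.5657)/0.5629 = −0.464, power 32.1% (plan: 32%).

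Both reproduce.

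**Step 2. Formula.** If a proportion *m* of an arm died before the window opened, the FAS percentage is *u*(1 − *m*). With survivors as denominator it is *u*.

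**Step 3. Day 28 upper bound.** Put all 28-day deaths before the window (*m* = 0.24 and 0.16). Survivors number 400 × 0.76 = 304 on placebo and 400 × 0.84 = 336 on ART-123.

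| Use among survivors, both arms (assumed) | Shown, placebo | Shown, ART-123 | False gap |
|---|---|---|---|
| 5% | 3.8% | 4.2% | 0.4 points |
| 10% | 7.6% | 8.4% | 0.8 points |
| 20% | 15.2% | 16.8% | 1.6 points |
| 30% | 22.8% | 25.2% | 2.4 points |

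The ART-123/placebo ratio is 0.84/0.76 = 1.105 for every *u*. With survivors as denominator the gap is 0.

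**Step 4. Why this is an upper bound.** The Day 28 window opens on Study Day 24, while 28-day mortality counts deaths through Study Day 29 (SAP 3.6.1 and its footnote). A subject given a vasopressor on or after Study Day 24 who then dies by Study Day 29 is still a user in the table. Only deaths before Study Day 24 matter. If 80% to 90% of 28-day deaths come before then (assumed):
- 80%: *m* = 0.192 and 0.128, ratio 0.872/0.808 = 1.079.
- 90%: *m* = 0.216 and 0.144, ratio 0.856/0.784 = 1.092.

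**Step 5. Earlier visits.** With half of the deaths before the window (12% vs 8%, assumed) the ratio is 0.92/0.88 = 1.045. With a quarter (6% vs 4%, assumed) it is 0.96/0.94 = 1.021. At baseline there is no effect, and at Day 1 very little.

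**Step 6. When the distortion is outweighed.** At the Step 3 rates the placebo figure stays below the ART-123 figure only while survivor use on placebo is less than 1.105 times that on ART-123. For example, 12% vs 10% among survivors prints as 9.1% vs 8.4%, in the true order.

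**The case against.** The strongest reply is that the FAS percentage is well defined: the share of all treated subjects in the arm who received an agent in the window. The survivor percentage conditions on a post-randomization outcome and does not guarantee a fair comparison. Suppose 20% of placebo survivors are on a vasopressor, and half of the 8 extra ART-123 survivors per 100 are too (both assumed). The survivor figures are then 20.0% vs (15.2 + 4)/84 = 22.9%, again against the arm with fewer deaths. This stands. It is why the numbers alive and dead belong beside the percentages, and why the survivor denominator cannot be presented as unbiased.

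The related information is also available elsewhere. Shock by visit uses survivors. Shock free and alive days (SAP 3.6.3 and 4.3.2.2) takes death into account. SAP 4.3.1.1 tabulates known dead, alive and unknown by arm at Study Days 7, 14 and 28, so a reader could re-base the percentages approximately. That limits the harm, but the table as specified still prints percentages that fall with deaths and do not share the shock table's basis.

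The distortion is also small against chance. The 1.6-point gap at 20% survivor use compares with a standard error of √[(0.152·0.848 + 0.168·0.832)/400] = 2.6 points, and no test is planned on this table.

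**Conclusion.** The point holds as a minor inconsistency in a descriptive table. Under SAP 4.1 and 4.2.7.3 as written, deaths before a visit window lower the displayed vasopressor use, and more so in the arm with more deaths. At the planning mortality rates and equal survivor use, the false ART-123/placebo ratio at Day 28 is at most 1.105, about 1.08 to 1.09 if 80% to 90% of deaths precede the window, and smaller earlier. These figures rest on planning mortality and on assumed survivor use and death timing. The primary result is unaffected.

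A reader might infer more than the documents support:
- **That the higher-mortality arm always looks better.** This holds only other things equal. Equal mortality removes the effect, and a large enough survivor difference outweighs it (Step 6).
- **That every death is scored as vasopressor-free, so use is understated by the full 24% and 16%.** Deaths inside a window do not exclude a subject from the numerator.
- **That the report would show two percentages for one fact.** The vasopressor table is by type of agent and plans no any-vasopressor row, so it repeats no row of the shock table. The bases differ, but the rows are not the same quantity.
- **That after-treatment major bleeding has the same fault.** SAP 4.4.6 says: "An after-treatment event is any event with an onset date of six or more days past last dose date". Its percentage of all treated subjects is a legitimate cumulative incidence, because a subject who died earlier did not have a late bleed. The documents also do not say what share of deaths falls before that period, so no size can be given. No change is called for there.

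**What to change.** Add to SAP 4.2.7.3 that the denominator at each post-baseline time point is the number of FAS subjects in the arm who are alive at that time point, with the numerator limited to those subjects, as in 3.6.4 and 4.3.3.2. Show the number alive and the number dead by arm beside the percentages at each visit.

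The cost is one sentence of SAP wording and a denominator already to be programmed for the organ dysfunction table. It needs no new data and no design change. The drawback is that the percentages then condition on survival, which the counts alive and dead make visible.
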